10.4 Exploratory Efficacy Analyses

With the exception of the Borg scale (which is recorded twice at each relevant visit – pre and post 2MWD and 6MWD), an MMRM analysis using placebo and selected dose of Flebogamma[®] 5% DIF 2MWD data from Stages 1 and 2 combined, will be performed and LS means will be plotted by visit and treatment group for each of the exploratory efficacy variables listed in section 4.1.3.

Estimates of treatment effect will be presented by a comparison of the mean change in each exploratory parameter from baseline to week 52 for selected dose of Flebogamma[®] 5% DIF versus Placebo.

Estimates of sustained treatment effect will be presented by a comparison of the mean change in each exploratory parameter from baseline to weeks 64 (where applicable) and 72 for selected dose of Flebogamma[®] 5% DIF versus Placebo.

The MMRM analysis will be repeated for the Borg scale, but with adjustment for timepoint (pre or post) within each visit. The following estimates of treatment effect will be provided separately for 2MWD and 6MWD:

- 1. Difference in mean change in Borg scale recorded prior to 2MWD/6MWD, from baseline to week 52 for Flebogamma® 5% DIF versus Placebo.
- 2. Difference in mean change in Borg scale recorded post 2MWD/6MWD, from baseline to week 52 for Flebogamma® 5% DIF versus Placebo.
- 3. Difference in mean change in the post-pre Borg scores, from baseline to week 52 for Flebogamma® 5% DIF versus Placebo.

11 SAFETY ANALYSIS

Safety analyses are based on the Safety Population. All combined safety data from both Stage 1 and Stage 2 together will be summarized by treatment arm. Safety analyses will be performed according to the actual treatment received.

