3 STUDY DESIGN AND OBJECTIVES

3.1 Study Design

This is a phase II/III, multicenter, prospective, randomized, placebo-controlled, double-blind, parallel-group clinical study with an adaptive design (flexible group sequential design with

adaptive dose selection) to evaluate the efficacy and safety of Flebogamma® 5% DIF in subjects with post-polio syndrome (PPS).

This study will consist of two stages. The first stage (Stage 1) is for dose selection, and the second stage (Stage 2) is to establish the superiority (efficacy confirmation) of the selected Stage 1 dose of Flebogamma® 5% DIF in physical performance (Two Minute Walk Distance [2MWD]) as compared to placebo by combining both Stage 1 and Stage 2 data. Safety analysis will be based on the combined data from both stages.

At Stage 1, 126 subjects are planned to be randomized across trial sites located in Canada, Czech Republic, Denmark, Germany, Italy, Netherlands, Poland, Spain and the United States of America. Eligible subjects will be randomized with 1:1:1 ratio into one of three treatment arms:

- Flebogamma[®] 5% DIF 2 g/kg of body weight
- Flebogamma[®] 5% DIF 1 g/kg of body weight
- Placebo (Normal Saline Solution)

At the end of Stage 1 (when at least 80% of randomized subjects have finished the treatment period of Stage 1), a formal unblinded interim analysis will be performed by an independent Data Monitoring Committee (DMC). Based on the pre-defined criteria, one of the two active treatment arms will be selected to continue to Stage 2 of the clinical study.

At Stage 2, a separate cohort of 84 subjects are planned to be randomized with 1:1 ratio into one of two treatment arms:

- Flebogamma® 5% DIF selected dose from Stage 1
- Placebo (Normal Saline Solution)

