5 GENERAL STATISTICAL CONSIDERATIONS

Statistical analyses and data presentations will be generated using SAS version 9.2 or higher.

Unless otherwise noted, for continuous variables, descriptive statistics will include the number of non-missing values, mean, standard deviation, median, minimum and maximum. The minimum and maximum will be presented to the same number of decimal places to which the data were recorded, the mean and median will be presented to 1 decimal place more than the data were recorded and the standard deviation will be presented to 2 decimal places more than the data were recorded.

For categorical variables, descriptive statistics will include counts and percentages per category. Percentages will be presented to 1 decimal place. Percentages of 0 and 100 will be reported as whole numbers (i.e. "0%" and "100%", respectively).

Unless otherwise noted, all statistical inference will be tested at 2-sided with α =0.05. P-values will be presented to 4 decimal places and confidence intervals will be presented to the same number of decimal places as the corresponding point estimate.

Unless otherwise noted, all data collected in the electronic case report forms (eCRFs) or electronically transferred (such as central laboratory data) will be presented in data listings. Subjects will be identified in the data listings by subject number (which includes site number)

and grouped by treatment arm. All summaries and listings will be presented by treatment arm and by study stage (i.e., Stage 1, Stage 2, and Overall) if appropriate.

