5.3 Sample Size Considerations

The sample size of this clinical study has been calculated based on the primary efficacy endpoint (2MWD) at the end of the treatment period.

Baseline measure of 2MWD in patients with PPS has been estimated in about 120 meters with standard deviation

s between 24 and 28 meters. The standard deviations for change from baseline to week 3 and week 17 in 2MWD are in the range of 8 to 11 meters [Horemans HL, Nollet F, Beelen A, et al., Stolwijk-Swüste JM, Beelen A, Lankhorst GJ, et al., Horemans HL, Beelen A, Nollet F, et al]. In order to show the superiority of Flebogamma® 5% DIF over placebo, an effect size of 5% (6 meters) in change from estimated baseline in 2MWT (120 meters) is assumed.

A clinically relevant change in distance walked at the end of the treatment period (after 52 weeks of treatment) between groups (Flebogamma[®] 5% DIF versus placebo) has been stated to be 5%.

In order to show the treatment difference of 6 meters in 2MWD with a standard deviation of 11 meters, 99 subjects need to be randomised into one of three treatment arms in Stage 1 and 66 subjects need to be randomised into one of two treatment arms in Stage 2. To account for a 20% dropout rate, approximately 126 will be randomised into one of the three treatment arms (42 subject/arm) in Stage 1, and approximately 84 subjects will be randomised into one of the two treatment arms (42 subject/arm) in Stage 2.

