11.1 Adverse Events

Analysis of AEs will be primarily focused on a descriptive analysis of AEs, suspected adverse drug reaction (ADRs) and adverse reaction (AR). Safety assessment will be based on the prevalence of suspected ADRs and AR occurred during the clinical trial.

- Suspected ADRs are defined as AEs with a causal relationship to study treatment of "Definitely Related", "Probably Related", "Possibly Related" or "Doubtful/Unlikely Related".
- ARs are defined as AEs with a causal relationship to study treatment of "Definitely Related".

AEs will be classified according to their onset date/time into the following categories:

Treatment emergent AEs (TEAEs): AEs with an onset date/time between first study treatment date/time and final study visit date or a pre-existing AE that worsens in severity within the same time window.

TEAEs will be further classified as follows:

- o On-treatment TEAEs: TEAEs with an onset date/time between first study treatment date/time and last study treatment date +4 weeks.
- o Infusional TEAEs: TEAEs with an onset date/time between the start date/time of study treatment infusion and 72 hours post-completion of the infusion of total dose of study treatment during any of the 2-day infusion periods.
- Post-treatment TEAEs: TEAEs with an onset date/time after the last study treatment date/time +4 weeks.
- non-TEAEs: all other AEs i.e. AE which occur prior to the start of study treatment.

For the purposes of classifying AEs into the above categories, partial AE start and end dates will be imputed to allow comparison with the study treatment date start and end dates. Section 13.1.1 below presents the imputation rules. Note, the imputed dates will be used for classification purposes only and the original partial AE dates will be presented in data listings.

AEs will be coded using MedDRA dictionary version 17.1 and summarized (stage 1 and stage 2 combined) by treatment group, system organ class (SOC) and preferred term (PT) as follows:

- TEAEs:
 - On-treatment TEAEs
 - overall
 - by maximum severity
 - by maximum causal-relationship
 - **SAEs**
 - suspected ADRs
 - ARs
 - **AESIs**
 - suspected ADRs of Special Interest (SI),
 - ARs of SI

- o Post-treatment TEAEs
 - overall
 - SAEs
- Infusional TEAEs
 - overall
 - SAEs
 - suspected ADRs
- Non-TEAEs

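### Combined-stage safety tables set the unselected dose, which exists only in Stage 1, beside placebo and selected-dose groups that would also contain Stage 2 subjects

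*SAP*

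**What the plan says.** SAP 3.1 gives the two stages different arm structures. In Stage 1, "Eligible subjects will be randomized with 1:1:1 ratio into one of three treatment arms": 2 g/kg, 1 g/kg and placebo. In Stage 2, "a separate cohort of 84 subjects are planned to be randomized with 1:1 ratio into one of two treatment arms": the selected dose and placebo. SAP 5.3 plans 42 subjects per arm in each stage.

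On safety, SAP 3.1 says "Safety analysis will be based on the combined data from both stages". SAP 11 says "All combined safety data from both Stage 1 and Stage 2 together will be summarized by treatment arm". SAP 11.1 has adverse events "summarized (stage 1 and stage 2 combined) by treatment group, system organ class (SOC) and preferred term (PT) as follows". Laboratory and vital-sign summaries (SAP 11.2 and 11.3) do not repeat the pooling wording and are reached only by the general sentence in SAP 11.

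Two other places bear on this:

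- SAP 5 has a general rule: "All summaries and listings will be presented by treatment arm and by study stage (i.e., Stage 1, Stage 2, and Overall) if appropriate".
- SAP 10 analyses the primary endpoint stage by stage and limits combined-stage secondary and exploratory analyses to placebo and the selected dose. SAP 11 carries no such limit.

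**The concern.** The unselected dose contributes Stage 1 subjects only, while placebo and the selected dose contribute subjects from both stages. In a crude pooled table, any contrast involving the unselected dose therefore mixes the effect of dose with the effect of stage. Stage 2 subjects could never have been allocated to that dose, so this part of the comparison is not randomised.

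The contrast has some use in the plan. The safety objective in SAP 3.2.3 is framed as a comparison with placebo. Protocol 10.1.3 also calls for a separate summary of infusional adverse events that are more frequent on Flebogamma than on placebo. If that summary is built from pooled data, which events qualify for the unselected dose could depend partly on Stage 2 placebo subjects. The percentages in SAP 11.1 are crude subject percentages, with no stratification by stage.

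**Working it through.** **Inputs**
- Evaluable subjects: 99 in Stage 1 over three arms and 66 in Stage 2 over two arms, so 33 per arm per stage; 20% dropout (SAP 5.3).
- Allocation 1:1:1, then 1:1 (SAP 3.1).
- Over-running and under-running rules (SAP 5.4).
- Between-stage difference in incidence: not in the documents, so assumed below.
- Actual Stage 2 enrolment: not in the documents.

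**Step 1: reproduce the planned sizes.** 33/(1 − 0.20) = 41.25, rounded up to 42 per arm. Then 3 × 42 = 126 and 2 × 42 = 84, total 210. These match SAP 5.3. The placebo share is (42 + 42)/210 = 40%, matching the two fifths given in protocol 2.4.

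**Step 2: make-up of the combined safety columns at planned size.**

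| Column | Stage 1 | Stage 2 | Total | Stage 2 share |
|---|---|---|---|---|
| Placebo | 42 | 42 | 84 | 50% |
| Selected dose | 42 | 42 | 84 | 50% |
| Unselected dose | 42 | 0 | 42 | 0% |

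**Step 3: false difference when no arm has any effect.** Let incidence be r1 in every Stage 1 arm and r2 in every Stage 2 arm, with D = r1 − r2 and m Stage 2 placebo subjects.
- Pooled placebo = (42·r1 + m·r2)/(42 + m).
- Unselected dose = r1.
- Unselected minus placebo = D × m/(42 + m), which is D/2 at m = 42.

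The same expression holds against the selected dose, with m counted in that arm.

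| Assumed D (percentage points) | m = 0 | m = 21 | m = 42 |
|---|---|---|---|
| 10 | 0 | 3.3 | 5 |
| 20 | 0 | 6.7 | 10 |
| 30 | 0 | 10 | 15 |

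Example: assumed incidence of 30% in Stage 1 and 40% in Stage 2 gives pooled placebo (42 × 30% + 42 × 40%)/84 = 35%. The unselected dose is at 30%, so it looks 5 points better with no true effect. With Stage 2 at 20% it looks 5 points worse.

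**Step 4: effect of the running rules on the share.**
- Over-run of 10%: Stage 1 has 126 × 1.1/3 = 46.2 per arm, so the share is 42/(42 + 46.2) = 48%.
- Under-run with Stage 1 stopped at an assumed 80%: 100.8/3 = 33.6 per arm. The other 25.2 move to Stage 2, giving (84 + 25.2)/2 = 54.6 per arm, so the share is 54.6/(33.6 + 54.6) = 62%.

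**Step 5: selected dose versus placebo.** Both arms have the same planned Stage 2 share, because allocation is equal within each stage. The stage terms cancel and the distortion is zero.

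**Step 6: after the change.** In a Stage 1-only table the unselected dose (42) faces 42 concurrent placebo and 42 concurrent selected-dose subjects. No Stage 2 subjects enter, so the stage term vanishes.

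**The case against.** The strongest reply is that SAP 5 already provides by-stage output, and that the combined wording in SAP 11 merely names the overall column. SAP 11 does not say combined tables only, whereas SAP 10 uses that word when it means to exclude. This stands in part: a reader might infer a settled decision to omit by-stage safety tables, and the text does not go that far. But the SAP 5 rule is qualified. By-stage output is written out again for disposition, deviations, demographics and compliance (SAP 6, 7, 8.1, 9.2), while the specific safety text says only that stages are combined. The two should be reconciled.

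Several stronger readings are also tempting, and the documents do not support them:

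- **That the trial's only dose-safety comparison is compromised.** No final safety comparison of 1 g/kg with 2 g/kg is planned. SAP 5.4 makes absence of a safety concern a condition of the dose-selection rule, and that decision comes before Stage 2.
- **That the stages are known to differ through pandemic measures or termination handling.** No calendar dates are given for either stage, and the content of Annex 18 is not in the text. The termination arrangements in SAP 2 depend on whether a subject was on treatment or in follow-up, not on stage. Only the order of the stages is documented. Stratification, administration and total volume are the same in both.
- **That the comparators are in fact half Stage 2.** That is the planned share. SAP 3.0 postdates the decision to stop early, and neither document says whether anyone entered Stage 2.

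Finally, pooling is deliberate and has value. Confining the reader to Stage 1 tables would cut placebo from 84 to 42. At an assumed 1% event rate, the chance of seeing at least one placebo event falls from 1 − 0.99^84 = 57% to 1 − 0.99^42 = 34%. This stands, and it is why the combined tables should be kept alongside.

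**Conclusion.** The point holds as a correctable gap in the safety specification. As written, SAP 11 and 11.1 combine stages without restricting the tables to arms present in both, so the unselected dose is displayed against comparators that are 50% Stage 2 at planned size (about 48% to 62% under the running scenarios above). The false difference is D × m/(42 + m), or D/2 at planned size. D is unknown, so the point figures are illustrations and do not show that a material bias occurred. If nobody entered Stage 2, there is no bias.

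A reader might infer that the safety conclusion for the selected dose, or a type I error rate, is at risk. Neither is: selected dose versus placebo is balanced within stage, and safety is descriptive with no test. The change is still worth making because it costs little and SAP 10 already applies the same restriction to efficacy.

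**What to change.** In SAP 11 and 11.1:

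1. State that the by-stage presentation rule of SAP 5 applies to safety.
2. Add Stage 1-only three-arm tables for adverse events, laboratory data and vital signs. Name them as the primary basis for reading the unselected dose against placebo or against the other dose. Build the unselected-dose part of the protocol 10.1.3 summary of infusional events exceeding placebo on the same basis.
3. Keep the combined tables for selected dose versus placebo. If they carry an unselected-dose column, label it Stage 1 only, so that rare events stay visible without inviting a direct comparison.
4. If no subject entered Stage 2, say so and remove the pooling text.

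The cost is one further set of outputs from the same programs with a stage filter; no new data are needed. The drawback is a placebo comparator of about 42 in the Stage 1 tables.

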11.1 Adverse Events

Analysis of AEs will be primarily focused on a descriptive analysis of AEs, suspected adverse drug reaction (ADRs) and adverse reaction (AR). Safety assessment will be based on the prevalence of suspected ADRs and AR occurred during the clinical trial.

- Suspected ADRs are defined as AEs with a causal relationship to study treatment of "Definitely Related", "Probably Related", "Possibly Related" or "Doubtful/Unlikely Related".
- ARs are defined as AEs with a causal relationship to study treatment of "Definitely Related".

AEs will be classified according to their onset date/time into the following categories:

Treatment emergent AEs (TEAEs): AEs with an onset date/time between first study treatment date/time and final study visit date or a pre-existing AE that worsens in severity within the same time window.

TEAEs will be further classified as follows:

- o On-treatment TEAEs: TEAEs with an onset date/time between first study treatment date/time and last study treatment date +4 weeks.
- o Infusional TEAEs: TEAEs with an onset date/time between the start date/time of study treatment infusion and 72 hours post-completion of the infusion of total dose of study treatment during any of the 2-day infusion periods.
- Post-treatment TEAEs: TEAEs with an onset date/time after the last study treatment date/time +4 weeks.
- non-TEAEs: all other AEs i.e. AE which occur prior to the start of study treatment.

For the purposes of classifying AEs into the above categories, partial AE start and end dates will be imputed to allow comparison with the study treatment date start and end dates. Section 13.1.1 below presents the imputation rules. Note, the imputed dates will be used for classification purposes only and the original partial AE dates will be presented in data listings.

AEs will be coded using MedDRA dictionary version 17.1 and summarized (stage 1 and stage 2 combined) by treatment group, system organ class (SOC) and preferred term (PT) as follows:

- TEAEs:
 - On-treatment TEAEs
 - overall
 - by maximum severity
 - by maximum causal-relationship
 - **SAEs**
 - suspected ADRs
 - ARs
 - **AESIs**
 - suspected ADRs of Special Interest (SI),
 - ARs of SI

- o Post-treatment TEAEs
 - overall
 - SAEs
- Infusional TEAEs
 - overall
 - SAEs
 - suspected ADRs
- Non-TEAEs

Adverse events will be summarized by presenting, for each treatment group, the number and percentage of patients with any AE, any AE within each SOC and any AE within each PT (grouped by SOC).

For summaries by maximum severity, if a patient reported more than one AE with the same PT, the AE with the maximum severity will be presented. If the severity of an AE is missing, the severity will be treated as missing in summaries. If a patient reported more than one AE within the same SOC, the patient will be counted only once under the maximum severity within the SOC.

Corresponding reporting rules will be applied for summaries by maximum causal-relationship.

All AEs will be listed by treatment group and subject identifier. In addition, subjects with SAEs and AEs leading to premature discontinuation of treatment period from the study will be individually listed.

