AEs temporally associated to the infusion of the investigational products (*i.e.*, infusional AEs, including infusional suspected ADRs), will be summarized by presenting infusion/subject incidences and percentage and ordered by ordinal number of infusions, and listed. In addition, the infusion rate in effect at the time of onset of the AE, the time the AE is first reported, and the time the AE changes materially in intensity and/or resolves will be also reported and listed. In addition, AEs temporally associated to the infusion of the investigational products for which the incidence in the Flebogamma[®] 5% DIF exceeds the incidence in the placebo group will be summarized separately.

Subjects with a serious adverse event (SAE) or who withdraw from the study because of an AE will also be individually listed and summarized.

AEs for which the investigator causality assessment is missing or undetermined will be individually listed.

Vital signs during infusions:

Vital signs (T, RR, HR, SBP and DBP) will be listed for each clinical trial subject. In case a subject presents a clinically relevant abnormality of vital signs (based on the Investigator's judgment) during an infusion, the event will be flagged and reported as an AE temporally associated to the infusion. All vital signs will be evaluated for each subject and for each infusion.

Physical assessment:

Physical findings (normal and abnormal) will be listed for each clinical trial subject. Any clinically relevant abnormality (based on the Investigator's judgment) developed by individual during the clinical trial and not already present at baseline will be reported as AE.

Blood biochemistry and cell counts:

All clinical laboratory data for renal (creatinine, BUN and GFR), hepatic (ALT, AST, ALP and TBL) and haematological parameters (CBC including differential leukocyte count) will be listed for each clinical trial subjects. Laboratory results out of the normal range judged by the Investigator as clinically relevant will be considered AEs.

	Number	GLB-PRT-FLB-IG1104	Version	7.0	Status	Effective	Effective Date	07-Mar-2022
CIVILOLS	IG1104 - A n	multicenter, prospective, randomized, placebo-controlled,	, double-blind	l, parallel-gro	up clinical trial	to assess the efficacy		70 F 3 - 00 F
Bioscience Industrial Group	and safety or	of Immune Globulin Intravenous (Human) Flebogamma®	5% DIF in pa	tients with P	ost-Polio Syndı	ome	rage	108 01 122

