13 APPENDICES

13.1 Imputation rules

13.1.1 AE date imputation

The following rules will be applied to impute AE start/end dates when partial AE start/end dates have been recorded. The imputed dates will be used for the determination of treatment emergence of AEs only. The original partial AE dates will be presented in data listings.

AE start date imputation:

AE start date imputation will be based on a comparison of the partial AE start date and the treatment start date. Table 12-1 presents the notation that will be used to describe the rules for imputation of partial AE start dates.

Table 12-1 Notation for imputation of partial AE start dates

	Year	Month	Day
Partial AE start date	YYYY	MON	Not used
Study treatment start date	TRTY	TRTM	Not used

Table 12-2 presents a matrix of rules for the imputation of AE start dates.

Table 12-2 AE start date imputation

	MON Missing	MON < TRTM	MON = TRTM	MON > TRTM
YYYY MISSING	NULL Uncertain	NULL Uncertain	NULL Uncertain	NULL Uncertain
YYYY < TRTY	(D) = 01JULYYYY Before Treatment Start	(C)= 15MONYYYY Before Treatment Start	(C)= 15MONYYYY Before Treatment Start	(C)= 15MONYYYY Before Treatment Start
YYYY = TRTY	(B)= TRTSTD+1 Uncertain	(C)= 15MONYYYY Before Treatment Start	(A)= TRTSTD+1 Uncertain	(A)= 01MONYYYY After Treatment Start
YYYY > TRTY	(E)= 01JANYYYY After Treatment Start	(A)= 01MONYYYY After Treatment Start	(A)= 01MONYYYY After Treatment Start	(A)= 01MONYYYY After Treatment Start
Before Treatme	ent Start	Partial indicates date	prior to Treatment Sta	art Date
After Treatmen	t Start	Partial indicates date	after Treatment Start	Date
Uncertain		Partial insufficient to o	determine relationship	to Treatment Start

LEGEND:		
NULL	No imputation	
(A)	Max(01MONYYYY,TRTSTD+1)	
(B)	TRTSTD+1	
(C)	15MONYYYY	
(D)	01JULYYYY	
(E)	01JANYYYY	

- 1. If the AE start date year value is missing, the date uncertainty is too high to impute a rational date. Therefore, if the AE year value is missing, the imputed AE start date is set to NULL (i.e. no imputation).
- 2. If the AE start date year value is less than the treatment start date year value, the AE started before treatment. Therefore:
 - a. if the AE year is less than the treatment year and the AE month is missing, the imputed AE start date is set to the mid-year point (01JulYYYY).
 - b. else, if the AE year is less than the treatment year and the AE month is not missing, the imputed AE start date is set to the mid-month point (15MONYYYY).

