- 3. If the AE start date year value is greater than the treatment start date year value, the AE started after treatment. Therefore:
 - a. if the AE year is greater than the treatment year and the AE month is missing, the imputed AE start date is set to the year start point (01JanYYYY).
 - b. else, if the AE year is greater than the treatment year and the AE month is not missing, the imputed AE start date is set to the month start point (01MONYYYY).
- 4. If the AE start date year value is equal to the treatment start date year value:
 - a. and the AE month is missing or the AE month is equal to the treatment start month, the imputed AE start date is set to one day after treatment start.
 - b. else, if the AE month is less than the treatment start month, the imputed AE start date is set to the mid-month point (15MONYYYY).
 - c. else, if the AE month is greater than the treatment start month, the imputed AE start date is set to the start month point (01MONYYYY).

AE end date imputation:

For the purpose of date imputation, the study treatment follow-up period date is defined as the last available visit date, i.e. including unscheduled visits after the end of study visit.

If the AE end date month is missing, the imputed end date should be set to the earliest of the (study treatment follow-up period date, 31DECYYYY, date of death).

If the AE end date day is missing, the imputed end date should be set to the earliest of the (study treatment follow-up period date, last day of the month, date of death).

If AE year is missing or AE is ongoing, the end date will not be imputed.

If the imputed AE end date is less than the existing AE start date then use AE start date as AE end date.

Imputed AE date flag

If the year of the imputed date is not equal to YYYY then imputed date flag = Y, else if month of the imputed date is not equal to MON then imputed date flag = M, else if day of the imputed date is not equal to day of original date then imputed date flag = D, else imputed date flag = null. Imputed AE date flags will be created separately for both AE start and end dates.

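### In two partial-date patterns the SAP imputes an AE start of first dose plus one day, ignoring any recorded end date and, as SAP 11.1 is worded, making every such event infusional

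*SAP*

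**What the plan says.** **Imputed start date.** SAP 13.1.1 (Table 12-2 and the numbered rules below it) compares the recorded year and month of a partial AE start with the year and month of treatment start. When the years are equal and the AE month is missing or equals the treatment-start month, "the imputed AE start date is set to one day after treatment start". Other partial dates go elsewhere: to the first or the middle of the recorded month, to 1 January or 1 July, or to no date if the year is missing.

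**Use of the imputed date.** SAP 11.1 lists treatment-emergent, on-treatment, infusional, post-treatment and non-treatment-emergent events, and then says: "For the purposes of classifying AEs into the above categories, partial AE start and end dates will be imputed". SAP 13.1.1 says: "The imputed dates will be used for the determination of treatment emergence of AEs only".

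**Category definitions.** In SAP 11.1 an infusional event starts between the start of an infusion and 72 hours after completion of the total dose of a 2-day infusion period. A non-treatment-emergent event is one that occurs before the start of study treatment.

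**Causality.** SAP 11.1 states "Suspected ADRs are defined as AEs with a causal relationship to study treatment of" definite, probable, possible or doubtful/unlikely, and adds "Safety assessment will be based on the prevalence of suspected ADRs and AR occurred during the clinical trial". Protocol 10.1.3, like the synopsis, says: "AEs for which the investigator causality assessment is missing or undetermined will be individually listed". SAP 11.1 contains no such listing, and SAP section 12, on changes from the protocol analyses, mentions only the cytokines.

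**The concern.** Placing an unknown onset just after first dose is a sensible cautious choice for deciding treatment emergence. Two things go wrong around it.

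(a) The choice is made without looking at information that may settle the matter. AEs are collected from consent, and screening lasts up to 4 weeks. An event that begins and resolves in the same calendar month as first dose, but before it, is therefore quite possible. If only the start day is unknown, the rule overrides a known end date and gives an impossible sequence, with the start after the end.

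(b) The date chosen for one purpose is also made available for another. First dose plus one day is Day 2 of the first 2-day infusion, so an event placed there is automatically infusional. Infusional events are a distinct safety display in this trial. Protocol 10.1.3 orders them by infusion number and separately summarises those with a higher incidence on active treatment than on placebo. Artificial events at infusion 1 would enter both displays. Because 11.1 and 13.1.1 disagree on scope, two programmers could produce different infusional tables from the same data.

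The causality point is narrower: a listing promised in the protocol has no counterpart in the SAP.

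**Working it through.** The plan states no figure on this point. The check applies its rules and then compares the result with a benchmark.

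**1. How far the rule reaches.** Table 12-2 has 4 rows (year) by 4 columns (month), so 16 cells:
- year missing: 4 cells, no imputation;
- year before treatment year: 4 cells, 1 July or mid-month;
- year equal to treatment year: 2 cells give first dose plus one day, 1 gives mid-month, 1 gives the first of the month;
- year after treatment year: 4 cells, 1 January or the first of the month.

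So 2 of 16 cells give first dose plus one day by rule, 4 give no date and 10 give other dates.

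**2. Recorded end date.** Take a first dose on 14 March 2018, an AE start recorded as March 2018 with the day unknown, and a recorded end of 10 March 2018 (illustrative dates). The imputed start is 15 March 2018, five days after the event ended. By the imputed date the event is treatment-emergent; by its end date it occurred before treatment. The only consistency check in 13.1.1 runs the other way: it resets an imputed end date that precedes the start. This result is the same whichever wording governs scope, because treatment emergence is the use that 11.1 and 13.1.1 both allow.

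**3. Infusional status under the 11.1 wording.** Each infusion visit covers 2 consecutive days, with up to 13 visits at 4-week intervals (Protocol 4.4.2.3 and Table 6). Taking whole calendar days, the infusional window is Days 1 to 5 of each 28-day cycle: 2 infusion days plus 72 hours. First dose plus one day is Day 2 of cycle 1, so 100% of events in the two patterns are infusional.

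**4. Benchmark.** Assume onset is uniform over days from first dose, and average over all 365 first-dose dates in a non-leap year.

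*Day missing, treatment-start month.* With R days left in the month, including the day of first dose, the infusional days are min(R, 5), plus R − 28 if R > 28. Summing over R:
- 31-day month: 151 infusional of 496 days;
- 30-day month: 143 of 465;
- 28-day month: 130 of 406.

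Over the year: (7 × 151 + 4 × 143 + 130) / (7 × 496 + 4 × 465 + 406) = 1,759 / 5,738 = 0.307.

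*Month missing, treatment-start year.* There are 365 × 366 / 2 = 66,795 date pairs. The 65 infusional days (13 × 5) contribute 65 × 365 − (5 × 28 × 78 + 13 × 10) = 23,725 − 11,050 = 12,675, where 78 is the sum of 0 to 12 and 10 the sum of 0 to 4. The share is 12,675 / 66,795 = 0.190.

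The rule therefore gives 100% where uniform onset would give about 31% and 19%.

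**5. All partial dates after first dose, Week 0 to Week 76 (533 days).** The uniform share is 65 / 533 = 12.2%.

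| Missing part | Placed on Day 2 of infusion 1 | Infusional after imputation | Infusional if uniform |
|---|---|---|---|
| Day only | 3.1% | 15.0% | 12.2% |
| Day and month | 34.5% | 44.8% | 12.2% |

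The third column also includes imputed first-of-month and 1 January dates that happen to fall in a later window. When only the day is missing, the overall effect is slight; it is large only when the month is missing too.

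**6. Causality.** The four grades in SAP 11.1 match Protocol 9.3.3. An event with no grade meets none of them and so is absent from the suspected-ADR tables. It stays in the overall tables of treatment-emergent events and in the listing of all AEs. For the maximum-severity table the SAP says "If the severity of an AE is missing, the severity will be treated as missing in summaries", and then "Corresponding reporting rules will be applied for summaries by maximum causal-relationship", so the event appears as missing in the causality table.

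**The case against.** The strongest reply is that 13.1.1 already says what is needed, since it restricts imputed dates to treatment emergence. The 11.1 sentence gives its purpose as comparison with the treatment start and end dates, which fits the treatment-emergent, on-treatment and post-treatment classes. Infusional status needs an onset date and time against each infusion period, and Table 12-2 supplies no time. The narrow use may well be what was intended. That much stands, but the sentence as written covers a list that includes infusional events. Read literally, 13.1.1 would in turn bar imputed dates from on- and post-treatment status, which 11.1 plainly wants. The two need reconciling either way. This reply does not touch the end-date gap.

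A second reply is that keeping undated events out of the infusional table could undercount a recognised IVIG risk. That is fair, and it is why those events should be listed separately.

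Some stronger readings are tempting but not supported:
- *Partial start dates in general land on the first infusion.* They do not; two patterns do.
- *Events with missing causality are misfiled and ought to count as suspected ADRs.* The SAP's grades follow the protocol, the protocol chose individual listing, and the events remain visible in other displays. Protocol 9.3.3 on relationships that cannot be ruled out guides grading; it does not define a missing value. Re-counting is a preference.
- *Each missing grade lowers the suspected-ADR count by one.* SAP 11.1 counts patients by SOC and PT, so a count falls only if the patient has no other suspected ADR at that level.
- *Extra infusional events dilute the contrast between arms.* Similar additions in each arm would leave a risk difference roughly unchanged, and the safety analysis is descriptive.

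**Conclusion.** The point holds as a minor defect in two stated rules. First, in the two partial-date patterns, an AE known to have ended before first dose is classed as treatment-emergent, contrary to SAP 11.1; this follows from the text and needs no assumption. Second, SAP 11.1 and 13.1.1 conflict on what imputed dates are for. Under the 11.1 wording all events in those patterns become infusional, against roughly 19% to 31% if onset were uniform over days and the window is taken as five calendar days per 28-day cycle. Those percentages are a benchmark only, since real onsets may cluster around infusions. Under the 13.1.1 wording this second problem does not arise.

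On causality, what remains is that the SAP omits a listing the protocol promises.

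The documents do not say how many AE records have partial dates or missing causality. Investigators must grade every AE, so missing grades should be uncommon, and the total impact is probably small. Nothing here bears on the efficacy analyses.

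**What to change.** **SAP 13.1.1:** do not impute a start date later than a recorded end date, and class an AE whose recorded end date is before first dose as non-treatment-emergent.

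**SAP 11.1:** use imputed start dates for treatment emergence and for on- or post-treatment status only, and align the scope sentence in 13.1.1 with this. Set infusional status only from the recorded parts of the date or from eCRF infusion data. List separately the events whose infusional status cannot be determined.

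**SAP 11.1, causality:** add the protocol's individual listing of AEs with missing or undetermined causality. A sensitivity table counting them as suspected ADRs is optional.

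**Cost:** a few sentences, small changes to two derivations and two listings, with no new data. The downside is that a few events with unknown onset day leave the infusional table; the separate listing keeps them visible.
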